4.3.10 Discontinuation Due to Confirmed Complete Response

Subjects with a CR may continue to receive study therapy until response confirmation or for an additional 2 cycles (whichever is longer) and then enter the follow-up period.

4.3.11 Stopping Rules for Clinical Deterioration

Accumulating evidence indicates that the emergence of objective responses to agents that activate anti-tumor immune responses may follow delayed kinetics of weeks or months, and can be preceded by initial apparent radiological progression or appearance of new lesions or some enlarging lesions while certain target lesions are regressing (“mixed response”). It is thus reasonable to allow for these possibilities and continue to treat the subject until progression is confirmed and found to be advancing and continuing at the next imaging assessment. These considerations should be balanced by clinical judgment as to whether the subject is clinically deteriorating and unlikely to receive any benefit from continued treatment. Such deterioration will be assessed to have occurred after a clinical event that, in the Investigator’s opinion, is attributable to disease progression, is unlikely to reverse with continued study treatment and therefore indicates that the subject is not benefiting from study treatment and cannot be managed by the addition of supportive care (such as bone directed radiotherapy, thoracentesis or paracentesis of accumulating effusions). The decision to continue or stop treatment should be discussed with the BMS Medical Monitor and will be documented in the study records.

4.3.12 Prophylactic and Acute Management of Infusion Reactions

Infusion reactions should be graded according to CTCAE Version 4.0 allergic reaction/hypersensitivity. These reactions may manifest with signs and symptoms that may include, but are not limited to fever, chills, headache, rash, pruritus, arthralgias, hypo- or hypertension, bronchospasm or other symptoms. Severe infusion reactions require the immediate interruption of study drug therapy and permanent discontinuation from further treatment. Appropriate medical therapy including epinephrine, corticosteroids, intravenous antihistamines, bronchodilators, and oxygen should be available for use in the treatment of such reactions. Subjects should be carefully observed until the complete resolution of all signs and symptoms. Following an infusion reaction, subjects should be premedicated with acetaminophen and diphenhydramine for future treatments.

Nivolumab and ipilimumab contain only human immunoglobulin protein sequences. Nevertheless, infusion reactions have been observed, although they are rare. If such a reaction were to occur, it might manifest with fever, chills, rigors, headache, rash, pruritis, arthralgias, hypotension or hypertension, bronchospasm, or other symptoms. All Grade 3 or 4 infusion

reactions should be reported within 24 hours to the BMS Medical Monitor and reported as a SAE if criteria are met. Infusion reactions should be graded according to NCI CTCAE (version 4.0) guidelines.

Treatment recommendations are provided below and may be modified based on local treatment standards and guidelines, as appropriate:

For Grade 1 symptoms: (Mild reaction; infusion interruption not indicated; intervention not indicated)

The following prophylactic premedications are recommended for future infusions: diphenhydramine 50 mg (or equivalent) and/or paracetamol 325 to 1000 mg (acetaminophen) at least 30 minutes before additional study drug administrations.

For Grade 2 symptoms: (Moderate reaction requires therapy or infusion interruption but responds promptly to symptomatic treatment [eg, antihistamines, non-steroidal anti-inflammatory drugs, narcotics, corticosteroids, iv fluids]; prophylactic medications indicated for ≤ 24 hours)

Stop the study drug infusion, begin an IV infusion of normal saline, and treat the subject with diphenhydramine 50 mg IV (or equivalent) and/or paracetamol 325 to 1000 mg (acetaminophen); remain at bedside and monitor subject until resolution of symptoms. Corticosteroid therapy may also be administered as appropriate. If the infusion is interrupted, then restart the infusion at 50% of the original infusion rate when symptoms resolve. Monitor subject closely. If symptoms recur then no further study drug will be administered at that visit. Subsequent infusions should be administered over 2 hours. The amount of study drug infused must be recorded on the case report form (CRF). The following prophylactic premedications are recommended for future infusions: diphenhydramine 50 mg (or equivalent) and/or paracetamol 325 to 1000 mg (acetaminophen) should be administered at least 30 minutes before additional study drug administrations. If necessary, corticosteroids (recommended dose: up to 25 mg of SoluCortef or equivalent) may be used.

For Grade 3 or Grade 4 symptoms: (Severe reaction, Grade 3: prolonged [ie, not rapidly responsive to symptomatic medication and/or brief interruption of infusion]; recurrence of symptoms following initial improvement; hospitalization indicated for other clinical sequelae [eg, renal impairment, pulmonary infiltrates]. Grade 4: life-threatening; pressor or ventilatory support indicated). Immediately discontinue infusion of study drug. Begin an IV infusion of normal saline, and treat the subject as follows: recommend bronchodilators, epinephrine 0.2 to 1 mg of a 1:1,000 solution for subcutaneous administration or 0.1 to 0.25 mg of a 1:10,000 solution injected slowly for IV administration, and/or diphenhydramine 50 mg IV with methylprednisolone 100 mg IV (or equivalent), as needed. Subject should be monitored until the investigator is comfortable that the symptoms will not recur. Study drug will be permanently discontinued. Investigators should follow their institutional guidelines for the treatment of anaphylaxis. Remain at bedside and monitor subject until recovery from symptoms. In the case of late-occurring hypersensitivity symptoms (eg, appearance of a localized or generalized

pruritus within 1 week after treatment), symptomatic treatment may be given (eg, oral antihistamine, or corticosteroids).

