4.3.5 Study Drug Discontinuation Criteria due to Adverse Event(s)

Study drug administration must be discontinued if at least one of the following drug related adverse event(s) occurs:

- Any \geq Grade 2 eye pain or reduction of visual acuity that does not respond to topical therapy and does not improve to Grade 1 severity within 2 weeks of starting therapy OR requires systemic treatment;
- Any \geq Grade 3 non laboratory drug-related adverse event with the exception of fatigue, and endocrine drug related AEs which are stable with hormone replacement therapy
- Any \geq Grade 3 bronchospasm, hypersensitivity reaction, or infusion reaction;
- Any patient that experiences any grade allergic/infusion reaction while receiving study drug at a slower infusion rate and/or with premedication due to a prior allergic/infusion reaction
- Any drug-related Grade 4 laboratory abnormalities, (except lymphopenia, asymptomatic lipase or amylase increases, or any electrolyte abnormality without any clinical sequelae that is either spontaneously reversible or resolves with clinical management to grade 2 or less within 72 hours)

- Hepatotoxicity as evidenced by any of the following:
 - AST or ALT > 5 - 10x ULN for >2 weeks
 - AST or ALT > 10 ULN
 - Total bilirubin > 5 x ULN
 - Concurrent AST or ALT > 3 x ULN and total bilirubin > 2 ULN (potential Hy's Law case)
- Any adverse event, laboratory abnormality or intercurrent illness, which in the judgment of the Investigator, presents a substantial clinical risk to the subject
- All adverse events that meet discontinuation criteria, as well as any Grade 3 or 4 infusion reactions must be reported to BMS, within 24 hours using the rapid notification procedures described in [Section 6.1.1](#).

Subjects who experience AEs that require discontinuation while receiving both nivolumab and ipilimumab may be allowed to continue therapy with nivolumab only if deemed in their best interest by both the PI and the BMS medical monitor. This will be decided on a case by case basis and will require convincing evidence that the benefit outweighs the risk.

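### Infusion reactions (Protocol 4.3.12): the Grade 2 steps let dosing resume at later visits after symptoms recur on restart, although the Grade 3 definition and Section 4.3.5 require the subject to stop

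*Protocol*

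**What the plan says.** Section 4.3.12 of the protocol sets out infusion-reaction management by grade. For Grade 2, the infusion is stopped and the subject is treated. If the infusion was interrupted, it restarts at 50% of the original rate when symptoms resolve. The paragraph continues: "If symptoms recur then no further study drug will be administered at that visit. Subsequent infusions should be administered over 2 hours". It then recommends premedication before future infusions.

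The Grade 3 or 4 paragraph follows directly. Among its Grade 3 criteria is "recurrence of symptoms following initial improvement", and its instruction is: "Study drug will be permanently discontinued". The opening of the same section has a general rule to the same effect: "Severe infusion reactions require the immediate interruption of study drug therapy and permanent discontinuation from further treatment".

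Section 4.3.5 lists drug-related events after which study drug must be discontinued. Two entries concern infusion reactions:

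- an event at or above "Grade 3 bronchospasm, hypersensitivity reaction, or infusion reaction";
- "any grade allergic/infusion reaction while receiving study drug at a slower infusion rate and/or with premedication due to a prior allergic/infusion reaction".

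It also sets a 24-hour reporting duty: "All adverse events that meet discontinuation criteria, as well as any Grade 3 or 4 infusion reactions must be reported to BMS". Section 3.5.1 includes adverse-event discontinuation under Section 4.3.5 among the reasons for stopping permanently.

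The graded steps in Section 4.3.12 are introduced with the words "Treatment recommendations are provided below and may be modified based on local treatment standards and guidelines, as appropriate". That section does not refer to Section 4.3.5.

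**The concern.** Consider a subject with a Grade 2 reaction whose symptoms resolve, whose infusion is restarted at half rate, and whose symptoms then return. The Grade 2 paragraph withholds drug for that visit only and goes straight on to later infusions over 2 hours with premedication. It does not exclude this subject from those infusions, and it does not tell the site to regrade. The Grade 3 paragraph and Section 4.3.5 say that the subject must stop.

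The main issue is safety: a site following the paragraph in front of it would re-dose someone whom the protocol elsewhere takes off treatment. If the site keeps the event at Grade 2, it may also miss the 24-hour report. The study has no data monitoring committee (Section 7), so such reports carry more weight.

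There is a secondary effect on the safety tables. Hypersensitivity/infusion reaction is a select adverse event category, tabulated by worst grade with a Grade 3-4 column (SAP 7.6.6). Events leading to discontinuation are tabulated in the same way (SAP 7.6.3). Parts 3 and 4 shorten the infusions to 30 minutes, and protocol Section 8.4.3 reviews infusion reactions to judge that change.

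**Working it through.** The plan states no figure on this point, so the main check is to apply each rule to the same event: a drug-related Grade 2 reaction, resolution, restart at 50% rate, recurrence.

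| Rule | Action |
|---|---|
| 4.3.12, Grade 2 paragraph | Stop for that visit; later infusions over 2 hours with premedication |
| 4.3.12, Grade 3 or 4 paragraph | Recurrence after improvement is Grade 3: permanent discontinuation |
| 4.3.12, opening paragraph | Severe reaction: permanent discontinuation |
| 4.3.5, Grade 3 or higher entry | Must discontinue |
| 4.3.5, slower-rate entry | Must discontinue at any grade, if the reaction earlier in the same visit counts as a prior one |

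The first row conflicts with the next three. The last row adds a further conflict only under the condition shown.

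**How many subjects.** The documents give no rate, so p, the proportion of subjects with a recurrence after restart, is assumed to be 0.5%, 1% or 2%. The denominators are planned numbers: 150 treated in all; about 50 with 30-minute infusions (Part 3: 20 + 10; Part 4: 10 + 10); about 10 in each of Arms B, D and E.

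Expected cases = n × p. Chance of at least one case = 1 − (1 − p)^n.

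| n | p = 0.5% | p = 1% | p = 2% |
|---|---|---|---|
| 150 | 0.75; 1 − 0.995^150 = 52.9% | 1.5; 1 − 0.99^150 = 77.9% | 3; 1 − 0.98^150 = 95.2% |
| 50 | 0.25; 22.2% | 0.5; 39.5% | 1; 63.6% |
| 10 | 0.05; 4.9% | 0.1; 9.6% | 0.2; 18.3% |

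**Effect of one case.** Suppose one event is read as Grade 3 with discontinuation instead of Grade 2 with continued dosing. The Grade 3-4 or discontinuation incidence then moves by:

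- 1/10 = 10 percentage points in Arm B, D or E;
- 1/20 = 5 points in Part 3 Arm A;
- 1/50 = 2 points in the pooled 30-minute group.

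The largest shift and the highest chance of a case belong to different denominators. A 10-point shift in one particular arm of 10 has a 4.9% to 18.3% chance of arising under these assumptions.

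**The case against.** The strongest reply is that the governing rule already exists. Section 4.3.5 is mandatory, while the graded steps are recommendations that sites may adapt. The hold for that visit could be read as a bedside instruction only, with later eligibility left to Section 4.3.5. On that reading all that is missing is a cross-reference. But a default step that departs from a mandatory stopping rule is still wrong as written, and the paragraph moves directly from recurrence to later infusions.

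A second reply separates improvement from resolution. The Grade 3 criterion would describe relapse of a reaction that had only partly settled, and the Grade 2 text would describe symptoms on rechallenge after full resolution. This does not work, because full resolution includes improvement and the criterion is met literally.

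A third reply is that a prior reaction in the slower-rate entry of Section 4.3.5 may mean one at an earlier visit. That reading is open, but the Grade 3 or higher entry applies without it. Section 4.3.5 also lets a subject on both drugs continue on nivolumab alone, case by case, with the agreement of the investigator and the medical monitor. The Grade 2 paragraph does not invoke that exception, and nivolumab monotherapy subjects cannot use it.

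Two points stand. The recurrence rates are assumptions. The effect on the tables is indirect: Section 4.3.12 has reactions graded by CTCAE version 4.0, so a site could record Grade 3 correctly and still follow the Grade 2 dosing step. In that case the dosing error remains and only the discontinuation counts are affected.

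**Conclusion.** The concern holds and should be fixed. For recurrence after restart, the Grade 2 paragraph gives a dosing instruction that contradicts the Grade 3 definition in the same section and the mandatory rule in Section 4.3.5. Taken together, the documents point to discontinuation, but no sentence says so for this case.

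The situation should be uncommon: 0.75 to 3 expected cases in 150 subjects under the assumed 0.5% to 2%. Its importance lies in avoidable re-exposure. The reporting effect is limited to grade-specific and discontinuation counts, where one case is visible in arms of 10 or 20. The overall infusion-reaction incidence, the primary biomarker endpoints and the sample size are unaffected.

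**What to change.** Amend the Grade 2 paragraph of Section 4.3.12 as follows:

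- If symptoms recur after restart, the reaction is Grade 3, study drug is permanently discontinued under Section 4.3.5, and the event is reported within 24 hours. The case-by-case nivolumab-only exception in Section 4.3.5 stays available to subjects receiving both drugs.
- Infusions over 2 hours with premedication apply only to Grade 2 reactions that do not recur after restart.
- For any reaction at a later visit under premedication or at a slowed rate, refer to Section 4.3.5.

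A bare cross-reference would cost less but would leave the contradictory step in place. The full change takes two or three sentences in a protocol amendment and needs no new procedures, data or subjects. The price is that a few subjects with a mild recurrence lose further dosing, which the Grade 3 definition and Section 4.3.5 already require.

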4.3.13 Guidelines for Management of Gastrointestinal, Pulmonary and Endocrine Adverse Events

All subjects who receive treatment on this study should be closely monitored for any signs related to gastrointestinal, pulmonary or endocrine systems and aggressively managed at the first onset of clinical symptoms. A high index of suspicion for colitis, endocrinopathy (e.g. hypothyroidism or adrenal insufficiency) or pneumonitis should be maintained in all subjects who present with any symptoms referable to these events, including but not limited to diarrhea, abdominal symptoms, fatigue, lethargy, weakness, dehydration or shortness of breath. Prompt initiation of appropriate diagnosis and therapy, including early administration of steroids, should be instituted. Guidance is provided in the appendix of the Nivolumab Investigator Brochure⁴⁸ and [Appendix 4](#).

4.4 Blinding/Unblinding

Not applicable for this study.

4.5 Treatment Compliance

Treatment compliance will be monitored by drug accountability as well as the subject's medical record and eCRF

4.6 Destruction and Return of Study Drug

4.6.1 Destruction of Study Drug

For this study, study drugs (those supplied by BMS or sourced by the investigator) such as partially used study drug containers, vials and syringes may be destroyed on site.

Any unused study drugs can only be destroyed after being inspected and reconciled by the responsible BMS Study Monitor unless study drug containers must be immediately destroyed as required for safety, or to meet local regulations (eg, cytotoxics or biologics).

On-site destruction is allowed provided the following minimal standards are met:

- On-site disposal practices must not expose humans to risks from the drug.
- On-site disposal practices and procedures are in agreement with applicable laws and regulations, including any special requirements for controlled or hazardous substances.
- Written procedures for on-site disposal are available and followed. The procedures must be filed with the site's SOPs and a copy provided to BMS upon request.
- Records are maintained that allow for traceability of each container, including the date disposed of, quantity disposed, and identification of the person disposing the containers. The method of disposal, ie, incinerator, licensed sanitary landfill, or licensed waste disposal vendor must be documented.
- Accountability and disposal records are complete, up-to-date, and available for the Monitor to review throughout the clinical trial period.

If conditions for destruction cannot be met, the responsible BMS Study Monitor will make arrangements for return of study drug.

It is the investigator's responsibility to arrange for disposal of all empty containers, provided that procedures for proper disposal have been established according to applicable federal, state, local, and institutional guidelines and procedures, and provided that appropriate records of disposal are kept.

4.6.2 Return of Study Drug

If study drug will not be destroyed upon completion or termination of the study, all unused and/or partially used study drug that was supplied by BMS must be returned to BMS. The return of study drug will be arranged by the responsible BMS Study Monitor.

It is the investigator's responsibility to arrange for disposal of all empty containers, provided that procedures for proper disposal have been established according to applicable federal, state, local, and institutional guidelines and procedures, and provided that appropriate records of disposal are kept.

4.7 Retained Samples for Bioavailability / Bioequivalence

Not applicable

5 STUDY ASSESSMENTS AND PROCEDURES

5.1 Flow Chart/Time and Events Schedule

Table 5.1A: CA209038 Screening Procedural Outline			
Procedure	Screening Visit	Visit 1 Day -3 to Day 1	Notes
Eligibility Assessments			
Informed Consent	X		A subject is considered enrolled only when a protocol-specific informed consent is signed
Inclusion/Exclusion Criteria	X		All inclusion/exclusion criteria should be assessed prior to study assignment
Medical History	X		Include all previous treatments, any toxicities or allergy related to previous treatments, history of tobacco use (how many packs for how many years) and other pulmonary history (e.g. asthma or toxic exposures)
BRAF mutation status	X		A hard copy of BRAF mutation status must be made available to the investigator and the Sponsor. For Part 1 only: If BRAF status is not known, then subjects' archival tumor tissue will be sent for centralized testing at a Sponsor-selected lab. Fresh tumor tissue should be used for BRAF mutation status only if the BRAF status is unknown, no archival tumor tissue is available and if there is adequate tumor tissue for all other tumor tissue assays.
Tumor tissue samples	X		For Part 1, must have lesions from which a minimum of 2 core biopsies for FFPE and RNA extraction can be taken. For Part 2 and 3, excisional/incisional biopsies preferred from non-lymph node lesion and tumor tissue samples will be centrally assessed for sufficient tumor content (≥ 100 tumor cells/4-micon section); subjects with samples that have insufficient tumor content will require re-biopsy prior to treatment. In Part 4, pre-treatment and on-treatment biopsies are optional; although strongly recommended if clinically safe. For Parts 1-4, archival tissue (FFPE block or a minimum of 10 unstained slides) should be obtained if available. See Section 5.6 for detail.
Blood Samples for Biomarkers	X		See Table 5.5A or Table 5.5B and Laboratory Manual for more details

Table 5.1A: CA209038 Screening Procedural Outline			
Procedure	Screening Visit	Visit 1 Day -3 to Day 1	Notes
Disease Assessments	X		CT chest, CT or MRI abdomen and pelvis, as well as MRI of brain should be performed if not performed within 28 days of anticipated drug administration.
Safety Assessments			
Assessment of Signs and Symptoms	X		Within 2 weeks prior to treatment; Record all medications taken within the prior 28 days as per Section 3.4
Concomitant Med Collection	X		Within 2 weeks prior to treatment; Record all medications taken within the prior 28 days as per Section 3.4
Physical Examination	X		To include height, weight
Vital Signs (including ECOG Performance Status)	X	X	Includes body temperature, respiratory rate, seated blood pressure and heart rate. Blood pressure and heart rate should be measured after the subject has been seated quietly for at least 5 minutes
Pulse oximetry	X		Collected at rest for at least 5 minutes. Oxygen levels will be used in combination with clinical signs and symptoms and radiographic images to evaluate pulmonary/respiratory status. Changes in O ₂ levels will not be used in isolation to document or diagnosis pulmonary toxicity
ECG	X		Single 12 lead measurement should be recorded after the subject has been supine for at least 5 minutes
Chest Radiograph	X		Unless performed within 30 days of anticipated first dose

Table 5.1A: CA209038 Screening Procedural Outline			
Procedure	Screening Visit	Visit 1 Day -3 to Day 1	Notes
Laboratory Tests (perform between day -14 to day -3)	X		To include CBC with differential, Complete Metabolic Panel (Na, K, Cl, CO ₂ , BUN or serum urea level, Cr, eGFR, AST, ALT, Alk Phos, Albumin, Total Bilirubin, Total Protein, Calcium, glucose), direct bilirubin, amylase, lipase, magnesium, phosphorous, LDH, TSH (with reflex to free T3 and free T4 if abnormal), adenocorticotrophic hormone (ACTH) collected in the morning (with reflex to cortisol if abnormal), Hep B surface Ag, Hep C antibody, HIV 1/2 antibody (may obtain additional testing or substitute testing per institutional guidelines to rule out infections), and urinalysis (dipstick); Subjects with suspected autoimmune thyroid disorders will also be tested for thyroid peroxidase antibodies and thyroid stimulating immunoglobulin
Serum or Urine Pregnancy Test	X		For WOCBP within 24 hours of Study Drug Administration
Follicle Stimulating Hormone (FSH) test (perform between day -14 to day -3)	X		Only required in certain instances in post-menopausal women. See Section 3.3.3 for criteria
Adverse Event Reporting			
Monitor for Serious Adverse Events	X	X	All SAEs must be collected from the date of the subject's written consent until 100 days post discontinuation of dosing or subject's participation in the study if the last scheduled visit occurs at a later time

Table 5.1B: CA209038 Treatment Procedural Outline, Part 1 (Cohorts 1 and 2)						
Procedure	Treatment Cycle = IV infusion q 2 weeks for 8 weeks				End of Treatment Visit	Notes
	Day 1	Day 15	Day 29	Day 43		
Safety Assessments						
Physical Examination	X	X	X	X	X	Done weekly in Cycle 1; to include body weight
Vital Signs (including ECOG Performance status)	X	X	X	X	X	Measured before and after study drug administration. Includes body temperature, respiratory rate, seated blood pressure and heart rate. Blood pressure and heart rate should be measured after the subject has been seated quietly for at least 5 minutes. Done weekly in Cycle 1 only.
Pulse oximetry	X	X	X	X	X	Collected at rest for at least 5 minutes, before each study drug administration. Oxygen levels will be used in combination with clinical signs and symptoms and radiographic images to evaluate pulmonary/respiratory status. Changes in O ₂ levels will not be used in isolation to document or diagnosis pulmonary toxicity.
Monitor for Adverse Events	X	X	X	X	X	All Non-Serious Adverse Events will be collected from Day1 until the subject's 100 days post discontinuation of dosing or subject's participation in the study if the last scheduled visit occurs at a later time All Serious Adverse Events must be collected from the date of the subject's written consent until 100 days post discontinuation of dosing or subject's participation in the study if the last scheduled visit occurs at a later time
Review Concomitant medications	X	X	X	X	X	
Laboratory Tests	X	X	X	X	X	To include CBC with differential, Complete Metabolic Panel (Na, K, Cl, CO ₂ , BUN, Cr, eGFR, AST, ALT, Alk Phos, Albumin, Total Bilirubin, Total Protein, Calcium, glucose), direct bilirubin, lipase, LDH, magnesium, phosphorus

Table 5.1B: CA209038 Treatment Procedural Outline, Part 1 (Cohorts 1 and 2)						
Procedure	Treatment Cycle = IV infusion q 2 weeks for 8 weeks				End of Treatment Visit	Notes
	Day 1	Day 15	Day 29	Day 43		
ECG	X				X	Single 12-lead ECGs will be collected at screening and prior to dosing on Day 1 of every other treatment cycle starting with Cycle 1. On Day 1 of Cycles 1, 2, and 4, an End of Infusion (EOI) ECG will be collected, as well. Electrocardiogram recording should be obtained just prior to as the serial PK samples as indicated in Table 5.5A.
Chest radiograph						As clinically indicated
Serum or Urine Pregnancy Test	X		X		X	Starting with Day 1 and then every other dose or every 28 days. For WOCBP within 24 hours of Study Drug Administration
Serum TSH	X					On Day 1 of each cycle
Exploratory						
Blood samples for PK, ADA, Biomarkers	See Table 5.5A for timing of samples					
Efficacy Response Assessments						
Disease assessment, Tumor Imaging (CT or MRI of Chest/Abdomen/Pelvis; MRI brain if clinically indicated)				X (between days 49-56)	X	Tumor assessments should be done every 8 wks (+/- 1 wk) until confirmed disease progression is documented or follow-up is completed. Methods used at baseline should be continued throughout study. MRI of brain are only required if clinically indicated
Clinical Drug						
Dispense Study Drug/Treatment	X	X	X	X		Nivolumab will be administered as an IV infusion on Days 1, 15, 29, 43 of each 56 day treatment cycle (8 weeks/cycle)

Table 5.1C: CA209038 Follow-up Visits - Part 1 (Cohorts 1 and 2)		
Procedure	Follow-up Visit 1 (40-60 days) and Visit 2 (101-120 days)	Notes
Safety Assessments		
Physical Examination	X	
Vital Signs (including ECOG)	X	Includes body temperature, respiratory rate, pulse oximetry, seated blood pressure and heart rate. Blood pressure, pulse oximetry and heart rate should be measured after the subject has been seated quietly for at least 5 minutes
Adverse Events Assessment	X	For study related adverse events only
Review Concomitant Medications	X	
Laboratory Tests	X	To include CBC with differential, Complete Metabolic Panel (Na, K, Cl, CO ₂ , BUN, Cr, eGFR, AST, ALT, Alk Phos, Albumin, Total Bilirubin, Total Protein, Calcium, glucose), direct bilirubin, lipase, LDH, magnesium, phosphorus, TSH
Serum or Urine Pregnancy Test	X	
ECG	X	12 Lead; for the first two follow-up visits only. Measurement should be recorded after the subject has been supine for at least 5 minutes
Tumor biopsy	X (encouraged, not mandated)	Upon confirmed progression May be done at either Follow-up visit 1 or Follow-up visit 2

Table 5.1C: CA209038 Follow-up Visits - Part 1 (Cohorts 1 and 2)		
Procedure	Follow-up Visit 1 (40-60 days) and Visit 2 (101-120 days)	Notes
Efficacy Assessments		
Disease assessment (CT/MRI)	X	Done after 12 weeks from the last on-study scan during Follow-up Visit 1 OR 2 then Q12wks by methods used at baseline Not required for subjects entering follow-up period for confirmed disease progression
Exploratory		
Blood samples for PK, ADA	X	As per Table 5.5A
Survival Status	X	Survival status should be continued every 3 months for the time remaining after the last office follow-up visit until 2 years from the first dose of BMS-936558 or until subject death, subject withdraws consent, subject is lost-to follow-up or the study is completed. This may be accomplished by visit or phone contact.

Table 5.1D: On Treatment Procedural Outline (CA209038) - Part 2, Part 3 and Part 4: Arms A and D								
[Procedure Window ± 2 days]								
Procedure	Wk1 Day 1	Wk4 Day 1	Wk7 Day 1	Wk10 Day 1	Wk 13 Day 1 and every 2 weeks thereafter	End of Therapy	Follow- Up Visits 1 and 2^a	Notes
Safety Assessments								
Targeted Physical Examination	X	X	X	X	X	X	X	To be performed only as clinically indicated
Vital Signs and Oxygen Saturation	X	X	X	X	X	X	X	Including BP, HR, temperature and oxygen saturation by pulse oximetry. Pulse oximetry at rest and after exertion within 72 hours prior to dosing
Physical Measurements (including performance status)	X	X	X	X	X	X	X	Weight and ECOG performance status
Adverse Events Assessment	X	X	X	X	X	X	X	Continuously throughout the study
Review of Concomitant Medications	X	X	X	X	X	X	X	
12 Lead ECG					X*			*To be performed pre-dose at Week 13, Week 23 and then every 16 weeks thereafter

Table 5.1D: On Treatment Procedural Outline (CA209038) - Part 2, Part 3 and Part 4: Arms A and D									
[Procedure Window ± 2 days]									
Procedure	Wk1 Day 1	Wk4 Day 1	Wk7 Day 1	Wk10 Day 1	Wk 13 Day 1 and every 2 weeks thereafter	End of Therapy	Follow- Up Visits 1 and 2 ^a	Notes	
Laboratory Tests									
Serum Chemistry	X	X	X	X	X		X	X	Within 72 hours prior to re-dosing to include: Aspartate aminotransferase (AST), Alanine aminotransferase (ALT), total bilirubin, alkaline phosphatase, lactate dehydrogenase, creatinine, blood urea nitrogen (BUN) or serum urea level, amylase, lipase, glucose, sodium, potassium, chloride, CO ₂ calcium, magnesium, TSH (if TSH is abnormal then obtain free T3 and free T4), ACTH collected in the morning as clinically indicated.
Hematology	X	X	X	X	X		X	X	Within 72 hours prior to re-dosing to include CBC with differential NOTE: Additionally required for the PBMC sample collection at the following timepoints: Week 1 Day 4; Week 2 Day 1; Week 3 Day 1; and Week 5 Day 1
Pregnancy Test (WOCBP only)	X	X	X	X	X	X	X	X	Serum or urine within 24 hours prior to administration of study drug

Table 5.1D: On Treatment Procedural Outline (CA209038) - Part 2, Part 3 and Part 4: Arms A and D								
[Procedure Window ± 2 days]								
Procedure	Wk1 Day 1	Wk4 Day 1	Wk7 Day 1	Wk10 Day 1	Wk 13 Day 1 and every 2 weeks thereafter	End of Therapy	Follow- Up Visits 1 and 2^a	Notes
Pharmacokinetic Samples								
PK samples								See Table 5.5C or Table 5.5E for schedule of samples
Other Samples								
Immunogenicity blood sample (ADA)								See Table 5.5C or Table 5.5E for schedule of samples
Biomarker Samples								See Table 5.5B for schedule of samples
Efficacy Assessment								
Tumor Assessment			X		X			Subsequent assessments at week 23, then every 8 weeks thereafter. May be obtained up to 7 days prior to the required visit. CT Chest and CT or MRI abdomen, pelvis and all known sites of disease. Use same imaging method used at screening. Arm D only, MRI brain also (subjects in other arms who have stable brain metastases should have surveillance brain MRI approximately every 16 weeks and as clinically indicated).

Table 5.1D: On Treatment Procedural Outline (CA209038) - Part 2, Part 3 and Part 4: Arms A and D								
[Procedure Window ± 2 days]								
Procedure	Wk1 Day 1	Wk4 Day 1	Wk7 Day 1	Wk10 Day 1	Wk 13 Day 1 and every 2 weeks thereafter	End of Therapy	Follow- Up Visits 1 and 2^a	Notes
Survival Data Collection							X	Survival status should be continued every 3 months for the time remaining after the last office follow-up visit until 2 years from the first dose of study drug or until subject death, subject withdraws consent, subject is lost-to follow-up or the study is completed. This may be accomplished by visit or phone contact.
Clinical Drug Supplies								
IVRS drug vial assignment	X	X	X	X	X			
Nivolumab Infusion treatment	X	X	X	X	X			
Ipilimumab Infusion treatment	X	X	X	X				

^a Follow up Visit 1 and 2 will occur at 40-60 days and 101-120 days after the stop of study therapy, respectively. Efficacy is required at Follow up visit 2 only.

Table 5.1E: On Treatment Procedural Outline (CA209038) - Part 3 and Part 4: Arms B and E^a				
[Procedure Window ± 2 days]				
Procedure	Wk1 Day 1 and every 2 weeks thereafter	End of Therapy	Follow- Up Visits 1 and 2^b	Notes
Safety Assessments				
Targeted Physical Examination	X	X	X	To be performed only as clinically indicated
Vital Signs and Oxygen Saturation	X	X	X	Including BP, HR, temperature and oxygen saturation by pulse oximetry. Pulse oximetry at rest and after exertion within 72 hours prior to dosing
Physical Measurements (including performance status)	X	X	X	Weight and ECOG performance status
Adverse Events Assessment	X	X	X	Continuously throughout the study
Review of Concomitant Medications	X	X	X	
12 Lead ECG	See note			To be performed pre-dose at week 13, week 23 and then every 16 weeks thereafter
Laboratory Tests				
Serum Chemistry	X	X	X	Within 72 hours prior to re-dosing to include: Aspartate aminotransferase (AST), Alanine aminotransferase (ALT), total bilirubin, alkaline phosphatase, lactate dehydrogenase, creatinine, blood urea nitrogen (BUN) or serum urea level, amylase, lipase, glucose, sodium, potassium, chloride, CO ₂ , calcium, magnesium, TSH (if TSH is abnormal then obtain free T3 and free T4), ACTH collected in the morning as clinically indicated.
Hematology	X	X	X	Within 72 hours prior to re-dosing to include CBC with differential NOTE: Additionally required for the PBMC sample collection at the following timepoints: Week 1 Day 4; Week 2 Day 1; and Week 4 Day 1

Table 5.1E: On Treatment Procedural Outline (CA209038) - Part 3 and Part 4: Arms B and E^a				
[Procedure Window ± 2 days]				
Procedure	Wk1 Day 1 and every 2 weeks thereafter	End of Therapy	Follow- Up Visits 1 and 2^b	Notes
Pregnancy Test (WOCBP only)	X	X	X	Serum or urine within 24 hours prior to administration of study drug
Pharmacokinetic Samples				
PK samples				See Table 5.5D for schedule of samples
Other Samples				
Immunogenicity blood sample (ADA)				See Table 5.5D for schedule of samples
Biomarker Samples				See Table 5.5B for schedule of samples
Efficacy Assessment				
Tumor Assessment	See Note			Assessments at week 7, 13, 23 and then every 8 weeks thereafter. May be obtained up to 7 days prior to the required visit. CT Chest and CT or MRI abdomen, pelvis and all known sites of disease. Use same imaging method used at screening. Arm E only, MRI brain also (subjects in other arms who have stable brain metastases should have surveillance brain MRI approximately every 16 weeks and as clinically indicated).
Survival Data Collection			X	Survival status should be continued every 3 months for the time remaining after the last office follow-up visit until 2 years from the first dose of study drug or until subject death, subject withdraws consent, subject is lost-to follow-up or the study is completed. This may be accomplished by visit or phone contact.
Clinical Drug Supplies				
IVRS drug vial assignment	X			
Nivolumab Infusion treatment	X			

- ^a Treatment Procedural Outline for subjects who progressed on Arm C.
- ^b Follow up Visit 1 and 2 will occur at 40-60 days and 101-120 days after the stop of study therapy, respectively. Efficacy is required at Follow up visit 2 only.

Table 5.1F: On Treatment Procedural Outline (CA209038) - Part 2, Part 3 and Part 4: Arms A, B, D, and E				
[Procedure Window ± 2 days]				
Procedure	Extension Period Starting at 2 years Every 2 weeks +/- 2 days	End of Therapy	Follow-Up Visits 1 and 2^a	Notes
Safety Assessments				
Targeted Physical Examination	X	X	X	To be performed only as clinically indicated
Vital Signs and Oxygen Saturation	X	X	X	Including BP, HR, temperature and oxygen saturation by pulse oximetry. Pulse oximetry at rest and after exertion within 72 hours prior to dosing
Physical Measurements (including performance status)	X	X	X	Weight and ECOG performance status
Adverse Events Assessment	X	X	X	Continuously throughout the study
Review of Concomitant Medications	X	X	X	Continuously throughout the study
12 Lead ECG	See note			To be performed every 16 weeks thereafter
Laboratory Tests				
Serum Chemistry	X	X	X	Within 72 hours prior to re-dosing to include: Aspartate aminotransferase (AST), Alanine aminotransferase (ALT), total bilirubin, alkaline phosphatase, lactate dehydrogenase, creatinine, blood urea nitrogen (BUN) or serum urea level, amylase, lipase, glucose, sodium, potassium, chloride, CO ₂ , calcium, magnesium, TSH (if TSH is abnormal then obtain free T3 and free T4), ACTH collected in the morning as clinically indicated.
Hematology	X	X	X	Within 72 hours prior to re-dosing to include CBC with differential
Pregnancy Test (WOCBP only)	X	X	X	Serum or urine within 24 hours prior to administration of study drug
Efficacy Assessment				
Tumor Assessment	X	X	X	Subsequent assessments at week 23, then every 8 weeks thereafter.

Table 5.1F: On Treatment Procedural Outline (CA209038) - Part 2, Part 3 and Part 4: Arms A, B, D, and E				
[Procedure Window \pm 2 days]				
Procedure	Extension Period Starting at 2 years Every 2 weeks +/- 2 days	End of Therapy	Follow-Up Visits 1 and 2^a	Notes
				May be obtained up to 7 days prior to the required visit. CT Chest and CT or MRI abdomen, pelvis and all known sites of disease. Use same imaging method used at screening. Arms D and E only, MRI brain also (subjects in other arms who have stable brain metastases should have surveillance brain MRI approximately every 16 weeks and as clinically indicated).
